The purpose of this study is to determine whether using CBCT to perform an abdomen-pelvis CT scan immediately following initial PCNL, before the patient emerges from general anesthesia, allows the surgeon to determine whether additional work is needed or whether the procedure can be concluded without requiring further imaging or future interventions. Therefore, the primary outcome will be the rate of subsequent surgical intervention (i.e. "second-look" interventions) in patients undergoing CBCT.

IV. Administrative Organization

This study will be performed exclusively in the Main Operating Room area of Loyola University Medical Center.

V. Study Design

1. The study population will be patients undergoing initial PCNL, and they will be recruited to participate in this study prior to surgery.
2. Outcomes from this study will be compared with existing data on rates of second-look intervention at this institution.
3. **Our retrospective chart review of PCNL patients from 2018 and 2019 revealed a total of 178 PCNL patients, with a second-look intervention rate of 31.5%. We anticipate that use of CBCT will reduce our second-look intervention rate to 10%. However, despite being rendered radiographically stone-free with CBCT, we imagine patients may require second-look procedures for various reasons; we estimate the upper bound of this occurrence to be 15%. Assuming this, along with a power of 80% and a type I error rate of 5%, our study would be appropriately powered with 39 patients. We will aim to recruit 60 patients to allow for redundancy and unanticipated exclusions such as for reasons listed in VI.1.i.2.**

VI. Study Procedures

1. Subject selection procedures
 - i. Sampling plan
 1. Inclusion criteria:
 - a. Patients >18yo
 - b. Undergoing initial PCNL
 - c. **Stone fragmentation (laser/ultrasonic/mechanical) was performed during the procedure**
 2. Exclusion criteria:
 - a. **Patients who are deemed by the operating surgeon not to require any form of CT imaging, intra-operatively or post-operatively (for example, this can occur in the event of a single visible stone which is removed in its entirety under direct vision without requiring any fragmentation)**
 - b. Patients whose procedures are aborted for various reasons, including but not limited to bleeding, hemodynamic instability, equipment failure, and inadequacy of nephrostomy access
 - c. Patients whose habitus does not allow for the use of the CBCT machine
 - ii. Recruitment procedures

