 1. **Patients undergoing initial PCNL will be recruited and provided protocol/consent materials at a preoperative**

outpatient clinic visit. Consent will be obtained by one of the research team members at the preoperative visit or in the preoperative area on the day of surgery.

2. The patient will not be required to attend any additional clinical appointments beyond standard care. The patient will not be compensated for their participation in the study.
2. Data collection procedures
 - i. **A retrospective chart review of first-look PCNL procedures from 2018-2019 will be performed to identify a matched-cohort (based on patient demographics and stone characteristics) that meets the inclusion and exclusion criteria.**
 - ii. Data will be prospectively collected for our study cohort. The determination of our primary outcome (need for repeat surgical intervention) will be made in our usual fashion: via shared decision-making between the patient and the surgical team on the day subsequent to the initial procedure.
 - iii. Data collected for both cohorts will include but not be limited to:
 1. Demographic factors (age, sex, race/ethnicity)
 2. Medical factors (patient height and weight, presence of medical comorbidities, surgical history, pertinent laboratory values)
 3. Stone factors (location, size, composition, and other characteristics)
 4. Surgical factors (length of procedure, blood loss, operative time, length of hospital stay, radiation dose)
 5. Surgical complications, ranked by Clavien-Dindo class
 - iv. All data will be entered into Loyola's secure RedCAP application.

VII. Safety Monitoring Plan

1. There are no additional anticipated patient safety issues associated with performing intra-operative CBCT when compared to standard post-operative CT imaging.
2. In another study using the same Medtronic O-arm CBCT system that is available at Loyola, it has been demonstrated that the radiation dose experienced by the patient from CBCT is lower than that from standard CT imaging.⁴

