3. In regards to radiation safety for operating room staff, standard precautions will be taken which include but are not limited to: using lead aprons for sterile surgical staff, optimizing the placement of sterile and non-sterile surgical staff, using lead aprons for sterile surgical staff, and standing beyond a 2-meter distance from the iso-centre. Assuming one CT per surgical procedure, a liberal average of three procedures per week, and 48 work-weeks per year, an unprotected staff member would be expected to receive below 1.6 mSv a year at a distance of 2-meters from the iso-centre.⁴ This is far below the occupational exposure limit set at 50 mSv per year by OSHA (Occupational Safety and Health Administration).

VIII. Analysis Plan

1. The historical cohort and study cohort will be compared on a variety of demographic and surgical factors to ensure homogeneity between the groups. Chi-squared and Student's t-tests will be performed as appropriate.
2. The proportion of patients requiring a second-look procedure would be calculated for both our cohort under study and our historical cohort. These proportions would be analyzed with a chi-squared test to determine statistical significance.
3. We would also perform subgroup analyses on a variety of patient characteristics, including but not limited to BMI, stone size, stone composition, and stone location, to determine if certain patient populations are more likely to benefit from CBCT.
4. Data will be analyzed by exporting tables from RedCAP onto Loyola's secure research network drives. From there, data will be imported into SPSS and analyzed as appropriate by the research team.

IX. Literature Cited

1. Pearle MS, Watamull LM and Mullican MA: Sensitivity of noncontrast helical computerized tomography and plain film radiography compared to flexible nephroscopy for detecting residual fragments after percutaneous nephrostolithotomy. *J Urol* 1999; 162: 23.

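### The cohort comparability check in VIII.1 uses surgical factors that are completed during or after the CBCT procedure, so it cannot show that the cohorts were alike before treatment

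*Combined protocol and SAP*

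**What the plan says.** Section VIII.1 (Analysis Plan) states that the historical and study cohorts "will be compared on a variety of demographic and surgical factors to ensure homogeneity between the groups", using chi-squared and t-tests. It names no individual factor and sets no threshold or consequence.

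The surgical factors are listed in one place, VI.2.iii.4: "Surgical factors (length of procedure, blood loss, operative time, length of hospital stay, radiation dose". That list sits under a lead-in that leaves it open: "Data collected for both cohorts will include but not be limited to".

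The same section collects preoperative information for both cohorts. VI.2.iii.2 has "Medical factors (patient height and weight, presence of medical comorbidities, surgical history, pertinent laboratory values", and VI.2.iii.3 has stone location, size, composition and other characteristics. VI.2.iii.5 adds, as a category of its own, "Surgical complications, ranked by Clavien-Dindo class".

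Comparability is also addressed in VI.2.i, where the 2018-2019 chart review is to yield a "matched-cohort (based on patient demographics and stone characteristics) that meets the inclusion and exclusion criteria".

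On how CBCT acts, Section III says the scan is done under the initial anaesthetic and "allows the surgeon to determine whether additional work is needed". Section II expects fewer later procedures and, as a result, a shorter hospital stay.

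**The concern.** A comparability check in a non-randomised study asks whether the groups were alike before the treatment under study could act. Variables measured after that point answer a different question, because they mix any initial difference with the effect of treatment. VIII.1 places such variables in the check.

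Two misreadings become possible. If CBCT works as hoped, a shorter stay or a longer operation could be taken as evidence that the cohorts were not comparable. If the surgical factors come out similar, that could be taken as reassurance about baseline, which it cannot give.

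The factors that would be informative are left unnamed. Comorbidities, surgical history and laboratory values appear in neither the matching nor VIII.1. BMI appears only as a subgroup factor in VIII.3. Stone characteristics are used for matching, but VIII.1 does not name them among the factors to be compared, so the plan does not say that balance on them will be shown.

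What is at stake is the interpretation of a historical comparison, and whether results on stay, operative time, blood loss and radiation are presented as results.

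**Working it through.** **Step 1. Timing of each listed surgical factor against CBCT.** The scan takes place within the index procedure and may lead the surgeon to keep operating (Sections II and III).

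| Factor (VI.2.iii.4) | Complete when | Support for a CBCT effect |
|---|---|---|
| Length of procedure | End of surgery, after the scan and any further work | Follows from the stated aim |
| Operative time | As above | Follows from the stated aim |
| Blood loss | As above | Plausible inference only |
| Radiation dose | After the scan, or later if postoperative CT is counted | Plausible inference; depends on which scans are counted, which is not defined |
| Length of stay | Discharge | Predicted in Section II |

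Five of five are completed during or after the procedure in which CBCT is used. None is a baseline variable.

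**Step 2. What Section VIII names.** Item 1 is the comparability check, item 2 the second-look proportion, item 3 subgroups by patient and stone characteristics, and item 4 data handling and software. None of the four names complications. None names comorbidities, surgical history or laboratory values.

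**Step 3. Illustration for length of stay.** The plan gives no figure to reproduce here. Inputs from V.3 are a historical second-look rate of 31.5%, an anticipated CBCT rate of 10% and an upper bound of 15%. Let D be the days a second look adds to the recorded stay. D is not in the documents; 1 to 3 days is assumed.

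Mean stay difference with identical baselines = (p_hist − p_CBCT) × D.

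- At 10%: (0.315 − 0.10) × D = 0.215 × D, giving 0.215, 0.430 and 0.645 days for D = 1, 2 and 3.
- At 15%: (0.315 − 0.15) × D = 0.165 × D, giving 0.165, 0.330 and 0.495 days.

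In patients, with 60 per cohort: 60 × 0.315 = 18.9 second looks historically, against 60 × 0.10 = 6.0 or 60 × 0.15 = 9.0 with CBCT. Sixty is the recruitment target; the matched cohort's size is not stated. The mean difference does not depend on cohort size.

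**Step 4. Would the planned t-test flag such a difference?** With 60 per group and a two-sided 5% test, the observed difference must exceed about 1.98 × SD × √(2/60) = 0.36 × SD. The SD of stay is not in the documents.

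- Assumed SD of 1 day: threshold 0.36 days. Three of the six values in Step 3 exceed it (0.430, 0.495 and 0.645).
- Assumed SD of 2 days: threshold 0.72 days. None exceeds it.
- Assumed SD of 3 days: threshold 1.08 days. None exceeds it.

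Step 3 therefore shows that a difference is expected without any baseline imbalance. It does not show that the test would detect it. No comparable figure can be derived for operative time, blood loss, radiation dose or complications.

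**The case against.** The strongest reply is that little depends on VIII.1. It sets no threshold, and no later step excludes, re-matches or adjusts on the surgical factors. The primary test in VIII.2 does not use them. Comparability is supported elsewhere, by matching on demographics and stone characteristics and by common eligibility criteria (VI.2.i), and VIII.1 itself includes demographic factors, which are valid baseline variables. The list in VI.2.iii is open, so an unlisted preoperative surgical factor could be intended. Much of the remedy is relabelling, since the same comparisons would be run.

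Most of this stands, and it limits the harm to interpretation. It does not rescue the rule as written: the stated purpose of the comparison is to establish homogeneity, every surgical factor actually listed is unfit for that purpose, and none that is fit is named.

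A reader might infer that a working intervention would necessarily be declared a failure of homogeneity. The text does not support that: VIII.1 names no individual factor and no decision rule, and Step 4 shows that the stay difference could well go undetected.

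A reader might also infer that the plan leaves complications out of the report. It does not say so. They are collected for both cohorts, and VIII.4 leaves further analysis to the team's judgement. On its own, the lack of a named analysis is missing detail rather than a wrong rule.

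**Conclusion.** The point holds as a fault in the comparability check. All five listed surgical factors are completed during or after the CBCT procedure, and the protocol itself predicts an effect on one of them. Differences on them could be misread as baseline imbalance, and similarity cannot establish prior comparability.

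It would go too far to conclude that the primary comparison is biased. The chi-squared test of second-look proportions does not depend on these factors, and the sample size is unaffected.

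The stay figures of 0.17 to 0.65 days are illustrative only. They rest on an assumed D of 1 to 3 days that is the same in both cohorts, on second-look days being counted in the recorded stay, and on the matched cohort keeping the 31.5% rate. That rate comes from all 178 patients in the chart review; the rate in the eligible, matched subset is not given. The conclusion about timing needs none of these assumptions.

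The change should be made: it is nearly free, and VIII.1 is the only comparability check that the analysis section describes.

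**What to change.** In VIII.1, limit the comparability check to preoperative demographic, medical and stone factors already collected under VI.2.iii, for example age, BMI, comorbidities, stone size and stone location.

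Add an item to Section VIII that reports operative time, blood loss, length of stay and radiation dose as secondary outcomes, with Clavien-Dindo complications alongside. Give each as a between-cohort difference with a 95% confidence interval, and state that these variables are not used for matching or adjustment. Define radiation dose the same way in both cohorts, saying which scans it covers.

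The cost is a few sentences and a modest amount of extra analysis. The items are already planned for collection in both cohorts, so no new data are needed beyond settling the radiation dose definition.

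### The primary comparison with a matched historical cohort is an unadjusted chi-squared test, so imbalance in predictive preoperative factors that matching leaves behind passes into the primary result

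*Combined protocol and SAP*

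**What the plan says.** - **Comparator.** The control data are a 2018-2019 chart review. Section V, item 3 reports that it "revealed a total of 178 PCNL patients, with a second-look intervention rate of 31.5" per cent. Section VI.2.i will use it to "identify a matched-cohort (based on patient demographics and stone characteristics) that meets the inclusion and exclusion criteria". No matching variables, ratio, caliper or algorithm are given.
- **Balance check.** Under VIII.1 the cohorts are "compared on a variety of demographic and surgical factors to ensure homogeneity between the groups", by chi-squared and t-tests. Nothing is said about what follows if they differ.
- **Primary test.** VIII.2 computes the two second-look proportions and continues: "These proportions would be analyzed with a chi-squared test to determine statistical significance".
- **Other use of covariates.** VIII.3 uses BMI and stone features for subgroup analyses, to see who benefits. It does not adjust the primary comparison. No regression, stratified, weighted, paired or sensitivity analysis of the primary outcome appears anywhere.
- **Data available.** VI.2.iii collects, in both cohorts, age, sex and race/ethnicity; "Medical factors (patient height and weight, presence of medical comorbidities, surgical history, pertinent laboratory values"; and "Stone factors (location, size, composition, and other characteristics".

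**The concern.** Without randomisation, a crude comparison of two proportions is unbiased only if the cohorts have the same mix of factors that predict a second look. Matching moves towards that, but matching by an unstated rule cannot be assumed exact, and it covers only the factors used. BMI may lie outside it. That is an inference: height and weight are filed under medical factors, while VI.2.i names demographics and stone characteristics.

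The check in VIII.1 does not close the gap. A significance test on cohorts of this size often misses a moderate difference, and no action is attached to a positive result. Part of what it names is also unsuitable for judging baseline balance. The surgical factors in VI.2.iii are "Surgical factors (length of procedure, blood loss, operative time, length of hospital stay, radiation dose", all of which arise during or after the operation and may themselves be changed by CBCT.

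This is the only planned test of the primary outcome. An imbalance could create an apparent benefit or hide a real one.

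**Working it through.** The plan gives no figure for confounding, so there is none to reproduce. The check asks what the planned test does when CBCT has no effect but the cohorts differ on one preoperative factor.

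**Inputs from the documents (V, item 3).** Control rate 31.5%; anticipated CBCT rate 10%, upper bound 15%; 39 patients needed, 60 to be recruited. The planned differences are 31.5 - 10 = 21.5 and 31.5 - 15 = 16.5 percentage points.

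**Assumptions, not in the documents.** One standardised factor X with odds ratio (OR) 2 or 3 per SD; X is g SD more favourable in the CBCT cohort; equal cohorts; two-sided 5%.

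**Step 1: bias.** Let logit P(second look) = a + ln(OR)·X, with X ~ N(0,1) in the historical cohort and N(-g,1) in the CBCT cohort. Choose a so that the historical rate is 31.5%. The bias is the CBCT-cohort rate minus 31.5%.

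**Step 2: type I error for a factor not matched on.** Sum the exact binomial probabilities of all 60 v 60 tables that the chi-squared rejects.

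| g (SD) | CBCT-cohort rate, OR 2 / OR 3 | Bias (points) | Two-sided error | Error favouring CBCT |
|---|---|---|---|---|
| 0 | 31.5% | 0 | 5.2% | 2.6% |
| 0.1 | 30.2% / 29.6% | -1.4 / -1.9 | 5.5% / 5.8% | 3.7% / 4.3% |
| 0.2 | 28.8% / 27.7% | -2.7 / -3.8 | 6.4% / 7.7% | 5.2% / 6.8% |
| 0.3 | 27.5% / 26.0% | -4.0 / -5.5 | 7.9% / 10.7% | 7.1% / 10.2% |

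At 39 v 39 the two-sided error is 6.1-6.9% at 0.2 SD and 7.0-8.8% at 0.3 SD. With a 0.3 SD gap against CBCT at 60 v 60, false positives favouring CBCT fall to 0.4-0.7%. A real benefit would be harder to show.

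**Step 3: a pair-matched factor.** Simulate 1:1 pairs alike on X (exactly, or within 0.2 SD) apart from the shift g, and apply the plain chi-squared. Ignoring the pairs makes the test conservative: with no gap, two-sided error is about 3.2-4.3%. At 60 v 60 it is about 5.2-5.5% at 0.2 SD and 6.8-8.2% at 0.3 SD. Error favouring CBCT still rises, to about 4.3-8.0% over those gaps, against a nominal 2.5%.

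**Step 4: can VIII.1 detect the gap?** For a t-test at 60 v 60 the noncentrality is g·√(60·60/120) = 5.48g, which is 1.10 at 0.2 SD and 1.64 at 0.3 SD. On 118 degrees of freedom, power is 19% and 37%. At 39 v 39 it is 14% and 26%.

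**Step 5: does adjustment work with so few events?** Expected events at a 10% CBCT rate:
- 39 v 39: 39·0.10 + 39·0.315 = 16.2
- 60 v 60: 60·0.10 + 60·0.315 = 24.9

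Firth logistic regression was simulated with cohort, three continuous covariates and one two-level covariate (independent cohorts, 10,000 trials per setting). Two-sided error was 4.4-5.4% at every gap from 0 to 0.3 SD, with no failed fits. Power at a 10% CBCT rate, chi-squared v Firth, was 67% v 67-71% (39 v 39) and 85% v 86-89% (60 v 60). At 15% it was 42% v 40-44% and 59% v 59-63%.

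**The case against.** **Matching is already planned, on the factors that matter most.** Age, stone size and stone location fall in the categories named in VI.2.i, and the eligibility criteria, including the exclusion for habitus (VI.1.i.2.c), apply to the historical cohort too. This stands in large part. For a pair-matched factor, a leftover gap up to 0.2 SD barely moves the two-sided error. The larger figures in Step 2 apply only to a factor outside the matching. BMI is a candidate by inference, and the habitus exclusion partly restricts it.

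**Larger inflation might be inferred.** If all 178 historical patients were the comparator, the same assumptions would give two-sided error up to 11.9% with a gap favouring CBCT and 14.3% with a gap against it. The documents do not support using these figures for the planned test. That comparison is unmatched, and 178 is the total before the eligibility criteria are applied.

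**VIII.1 may cover more than it names.** Its wording is open-ended and does not exclude stone factors. That is fair. The defects are that no action follows, and that surgical factors do not show baseline balance.

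**The remedy has its own error.** In the simulations the Firth risk difference was shrunk towards zero by about 0.5-1.7 points, similar to the bias from a 0.1 SD gap. At 39 v 39, a 15% rate and OR 2, its power was slightly lower (40.4% v 41.6%). Both stand, so Firth regression is an option and not a requirement.

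**The main threats may be unmeasured or calendar-time differences.** Adjustment does not remove these. They limit what any analysis of this design can claim, but are no reason to leave measured factors uncorrected.

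**Conclusion.** The concern holds as a moderate one that should be fixed before analysis. The primary test has no correction for measured imbalance, and the balance check cannot be relied on to reveal it. Under the stated assumptions at 60 v 60, a 0.2-0.3 SD gap in an unmatched predictor shifts the difference by 2.7-5.5 points, against a planned 16.5-21.5, with two-sided error of 6.4-10.7%. For a pair-matched predictor the error is near nominal at 0.2 SD and modestly raised at 0.3 SD, although false positives favouring CBCT still increase. At 0.1 SD the two-sided inflation is under one point in either case.

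The gaps and odds ratios are assumed, so these figures show how sensitive the test is and do not predict its bias. A reader might infer that the result will be biased towards CBCT, or that the matching is inadequate. The documents support neither: the direction is unknown, and the matching rule is unstated, not shown to fail. Nor is ignoring pairs a source of false positives, since that makes the test conservative.

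**What to change.** Keep the matched cohort of VI.2.i and the chi-squared test, and make these changes:

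1. **VI.2.i:** state the matching variables, ratio and rule.
2. **VIII.2:** prespecify a covariate-adjusted comparison of second-look rates as the main estimate, reported as an adjusted difference with a 95% CI beside the chi-squared. Use a short preoperative list, for example stone size, BMI and age as continuous terms and stone location in two levels. Fit logistic regression, penalised (Firth) if events are few and the software allows, or use fewer covariates. If the cohort is pair-matched, use an analysis that respects the pairs.
3. **VIII.1:** judge baseline balance on preoperative factors, by standardised differences. Report procedure length, blood loss, stay and radiation dose as outcomes.
4. **Limitations:** state that unmeasured and calendar-time differences between 2018-2019 and the study period remain.

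The cost is wording and a covariate list, with no new data. The headline analysis becomes slightly more complex, and a Firth estimate is slightly shrunk. With about 16 to 25 events the list must stay short. In simulations at a 10% CBCT rate and OR 3, ordinary logistic fits with location at four assumed levels failed in 25% of trials at 39 v 39 and 9% at 60 v 60, against 1.8% and 0.2% with two levels. VIII.4 names SPSS, so check whether the version in use fits penalised models. Using all eligible historical patients instead would replace the matched design. That is a separate trade-off which this fix does not need.
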